Serious events of diarrhea were reported by 21 subjects (10% of dosed subjects) in the CMX001-304 study. GI events were the most frequently reported AEs that led to BCV discontinuation (16% adults, 5% pediatric subjects); more specifically, diarrhea prompted BCV discontinuation in 9% adults and 5% of pediatric subjects, followed by abdominal pain (6% adults vs. < 1% pediatric subjects). Overall, more adult subjects (34%) than pediatric subjects (19%) discontinued treatment with BCV due to any AE.

Based on learnings to-date, it is recommended that BCV be interrupted for treatment-emergent diarrhea of \geq CTCAE (National Institutes of Health/National Cancer Institute Common Terminology Criteria for Adverse Events) Grade 2, with a treatment interruption of at least 7 days (i.e., at least 6 full days off drug) and until symptoms improve to \leq Grade 1. In doing so, interruption of BCV treatment serves as both a diagnostic test and, if the diarrhea is related to BCV, the time off drug also allows the gut epithelium an opportunity to regenerate. If the diarrhea improves, BCV may be safely reintroduced thereafter. A dose consolidation approach (administering the same total weekly dose at weekly dosing intervals to allow more time between doses for GI mucosal regeneration) is also recommended at re-introduction of BCV. If there is no improvement following interruption of BCV, the likely etiology of diarrhea is not BCV;

nevertheless, BCV should not be reintroduced until the diarrhea improves, regardless of the underlying etiology.

In conclusion, oral administration of BCV is associated with known GI toxicity, which cannot be reliably differentiated from GI GVHD histopathologically or based on GI symptoms. Though clinical evaluation of other organ systems also affected by GVHD, namely the skin, may assist in determining the most appropriate patient management strategy, treatment-emergent diarrhea of Grade 2 or higher severity, regardless of etiology, should prompt BCV treatment interruption for at least 7 days (i.e., 6 full days off drug). Initiation of steroid therapy for GVHD should be delayed, if clinically appropriate, in order to assess whether symptoms improve as a result of BCV withdrawal. Resumption of BCV as a consolidated QW dose is possible if symptoms improve.

Further details of this and other BCV-related toxicities are provided in the BCV Investigator's Brochure.

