4.3.1. Study Rationale

Allogeneic HCT recipients are at risk of AdV infection and disease progression. Published guidelines recommend screening of high-risk HCT recipients and the application of antiviral therapy pre-emptively before AdV disease occurs. However, there is currently no approved antiviral therapy for AdV.

BCV is an investigational antiviral which has demonstrated activity against AdV in vitro and in clinical investigations. In previous studies of oral BCV for AdV infection, initiation of therapy early in the course of infection (when plasma viral load was less than 10^4 or 10^5 copies/mL) was associated with rapid clearance of viremia.

As described previously, diarrhea is the most common AE associated with oral BCV administration with typical onset in pediatric subjects from 4 to 6 weeks after initiating treatment with BCV. In the context of HCT, BCV-related diarrhea can mimic symptoms of GI GVHD, which can confuse accurate diagnosis and management of patients (Detweiler 2016). GI toxicity management that was conservative (i.e., specifically withholding further BCV dosing until symptoms resolved) appeared to be an effective and straightforward toxicity management approach, and was associated with better subject outcomes in Study CMX001-301 (Marty 2016). As described in Section 4.2.3.1, these clinical findings have led to further refinement of the

subject safety monitoring and management guidance for oral BCV to promote a more conservative management approach with clear and mandated stopping criteria. The assessment of the effectiveness of these revised guidelines as a critical component in optimally managing subjects is a primary objective of this study.

Therefore, this study is designed to assess the safety and overall tolerability of oral administration of BCV using defined safety monitoring and management criteria (Section 8.3) and to assess the impact of BCV in reducing AdV viremia in HCT recipients relative to the current SoC. By studying the proposed treatment paradigm and toxicity management in a subject population likely to benefit from treatment, a more refined approach to overall treatment strategies can be established.

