7.2. Subject Exclusion Criteria

Subjects who meet *any* of the following criteria, as applicable, are not eligible to participate in this study. Retesting of exclusionary laboratory results (through the designated central laboratory) is permitted.

[Note: The CTCAE grading scales for diarrhea ([Table 7](#)) and the NIH staging scales for acute GVHD ([Appendix 1](#)) will be used to determine eligibility into this study. Current stool output or volume, as appropriate, should be compared with each subject's pre-transplant stool output or volume (= baseline). Contact the Chimerix Medical Monitor (or designee) for eligibility questions where baseline stool output or volume is unknown or the subject's clinical condition warrants consideration of an alternative baseline measure.]

1. Any CTCAE Grade 4 diarrhea (i.e., life-threatening consequences with urgent intervention indicated) within 7 days prior to Day 1
2. Any CTCAE Grade 2 or 3 diarrhea (i.e., increase of ≥ 4 stools per day over baseline), unless attributed to AdV, within 7 days prior to Day 1
3. NIH Stage 4 acute GVHD of the skin (i.e., generalized erythroderma with bullous formation) within 7 days prior to Day 1
4. NIH Stage 2 or higher acute GVHD of the liver (i.e., bilirubin > 3 mg/dL [SI: > 51 $\mu\text{mol/L}$]) within 7 days prior to Day 1
5. NIH Stage 2 or higher acute GVHD of the gut (i.e., diarrhea > 556 mL/m²/day, or severe abdominal pain with or without ileus) within 7 days prior to Day 1

6. Active malignancy (with the exception of non-melanoma skin cancer), including relapse or progression of the underlying disease for which qualifying transplant was performed
7. Use of vasopressors within 7 days prior to Day 1
8. PT-INR > 2x upper limit of normal reference range (ULN) in the absence of anticoagulation within 7 days prior to Day 1
9. Requirement for mechanical ventilation within 7 days prior to Day 1, or sustained oxygen delivery for > 24 hours within 7 days prior to Day 1, or any oxygen requirement within 48 hours prior to Day 1
10. Estimated creatinine clearance < 30 mL/min or use of renal replacement therapy (e.g., hemodialysis, continuous renal replacement therapy, peritoneal dialysis) within 7 days prior to Day 1
11. ALT > 5x ULN, AST > 5x ULN, or total bilirubin > 3 mg/dL [SI: > 51 µmol/L] within 7 days prior to Day 1

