For subjects with CTCAE Grade 1 diarrhea or no diarrhea at baseline, BCV must be interrupted for treatment-emergent CTCAE Grade 2 or higher diarrhea. This includes new-onset Grade 2 or higher diarrhea or progression from Grade 1 to Grade 2 or higher diarrhea, regardless of the cause of the diarrhea.

In general, changing multiple therapies at the same time (e.g., interrupting BCV and starting steroids for new-onset or worsening GI GVHD) is not recommended. In order to assess response to BCV treatment interruption, start of (or increase in) steroid therapy for new-onset or worsening GI GVHD should be delayed, when possible.

- If diarrhea does not improve following ≥ 7 days interruption (at least 6 calendar days off BCV), a trial of steroid therapy for new-onset or worsening GI GVHD (while BCV is still being held) may be considered if deemed clinically appropriate.

If diarrhea does not improve to \leq CTCAE Grade 1 during interruption, BCV must not be resumed.

If diarrhea improves to \leq CTCAE Grade 1 in intensity, subjects may resume dosing of BCV, but no sooner than 7 days (i.e., at least 6 full days off drug) following the last BCV dose administration.

- If resumed, BCV must be administered in a consolidated QW dose (total weekly dose administered once weekly, i.e., 4 mg/kg, up to a maximum of 200 mg, QW in the absence of concurrent cyclosporine, or 2.8 mg/kg, up to a maximum of 140 mg, QW for subjects taking concurrent cyclosporine) to potentially improve tolerability, as weekly dosing intervals allow more time for GI mucosal regeneration between doses.

Treatment with the consolidated QW BCV dose will be continued through Week 16 post-randomization or until confirmed undetectable AdV viremia in plasma, whichever occurs first.

Recurrence of CTCAE Grade 2 or higher diarrhea after restarting BCV requires permanent discontinuation of BCV.

8.3.2.3. Treatment-emergent Diarrhea AEs in Subjects with Grade 2 or 3 Diarrhea Attributed to AdV at Baseline

For subjects with CTCAE Grade 2 or 3 diarrhea at baseline that is attributed to AdV, BCV dosing must be interrupted if:

- the diarrhea has not improved to \leq CTCAE Grade 1 after 21 days of therapy, or

- the subject experiences on-treatment worsening of one CTCAE grade or more at any time following initiation of BCV (i.e., Grade 2 worsens to \geq Grade 3, or Grade 3 worsens to \geq Grade 4), regardless of the cause of the diarrhea

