If the diarrhea does not improve during interruption, BCV must not be resumed.

If diarrhea improves to \leq Grade 1 in intensity during interruption, subjects may resume dosing, but no sooner than 7 days (i.e., at least 6 full days off drug) following the last BCV dose administration.

- If resumed, BCV must be administered in a consolidated QW dose (total weekly dose administered once weekly, i.e., 4 mg/kg, up to a maximum of 200 mg, QW in the absence of concurrent cyclosporine, or 2.8 mg/kg, up to a maximum of 140 mg, QW for subjects taking concurrent cyclosporine) to potentially improve tolerability, as weekly dosing intervals allow more time for GI mucosal regeneration between doses.

Recurrence of CTCAE Grade 2 or higher diarrhea after restarting BCV requires permanent discontinuation of BCV.

See [Table 8](#) and [Table 9](#) for tabular summaries of the interruption and discontinuation thresholds for managing BCV in the setting of treatment-emergent diarrhea and recommendations for the management/evaluation of treatment-emergent GI AEs during BCV therapy.

Table 8: BCV Interruption and Discontinuation Thresholds for Treatment-emergent Diarrhea

Action Taken with BCV	\leq Grade 1 Diarrhea at Baseline	AdV-related Grade 2 Diarrhea at Baseline	AdV-related Grade 3 Diarrhea at Baseline
Temporary interruption	
 Interrupt if diarrhea worsens to \geq Grade 2 Consider interruption for Grade 1 diarrhea if persists for > 14 days, and starting treatment for acute GVHD 	
 Interrupt if diarrhea not \leq Grade 1 within 21 days of first dose of BCV Interrupt if diarrhea worsens to \geq Grade 3 at any time 	
 Interrupt if diarrhea not \leq Grade 1 within 21 days of first dose of BCV Interrupt if diarrhea worsens to \geq Grade 4 at any time
Resumption	
 May resume if diarrhea improves to \leq Grade 1, and after a minimum 7-day interruption (i.e., at least 6 full days off BCV) Must resume at 4 mg/kg (max 200 mg) QW or 2.8 mg/kg (max 140 mg) QW with concurrent cyclosporine administration 		
Permanent discontinuation	
 Permanently discontinue BCV if, following resumption of dosing, diarrhea \geq Grade 2 returns 		

Grade 1: Increase of < 4 stools per day over baseline; or mild increase in ostomy output compared to baseline

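### For AdV-attributed diarrhea that improves on brincidofovir and then returns, Section 8.3.2.3 does not say which grade worsening is measured from, and the two readings give opposite interruption instructions

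*Combined protocol and SAP*

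**What the plan says.** Exclusion criterion 2 (Section 7.2) bars Grade 2 or 3 diarrhea "unless attributed to AdV, within 7 days prior to Day 1", so children with AdV-attributed Grade 2 or 3 diarrhea can be randomized.

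For these children Section 8.3.2.3 (and the Synopsis) gives two interruption triggers:

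- a time check: "the diarrhea has not improved to \leq CTCAE Grade 1 after 21 days of therapy";
- a worsening rule: "on-treatment worsening of one CTCAE grade or more at any time following initiation of BCV", followed by a parenthesis: "i.e., Grade 2 worsens to \geq Grade 3, or Grade 3 worsens to \geq Grade 4), regardless of the cause of the diarrhea".

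Table 8 sets the worsening threshold by entry grade. The Grade 2 column reads "Interrupt if diarrhea worsens to \geq Grade 3 at any time"; the Grade 3 column gives the same instruction at "Grade 4 at any time".

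Permanent discontinuation for returning diarrhea, in Section 8.3.2.3 and Table 8, applies only after BCV has been interrupted and restarted.

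Three other places bear on the point. Section 4.2.3.1 concludes that treatment-emergent diarrhea of "Grade 2 or higher severity, regardless of etiology, should prompt BCV treatment interruption for at least 7 days", with no exception by entry grade. Section 8.3.2.1 sends Grade 1 diarrhea that worsens to Grade 2 or more to Section 8.3.2.2, which by its heading and first sentence covers only subjects with Grade 1 or no diarrhea at baseline. Section 4.3.1 says BCV diarrhea has a "typical onset in pediatric subjects from 4 to 6 weeks after initiating" treatment.

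**The concern.** The worsening rule needs a reference grade and none is stated. This makes no difference for a child whose diarrhea never improves. It decides the action for a child whose diarrhea settles to Grade 1 or less without an interruption and then comes back. Two sites could treat the same child in opposite ways, each able to point to the protocol.

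The rule is part of what the trial is testing. Section 4.3.1 makes the effectiveness of the revised toxicity guidance a primary objective, and Section 4.4 presents the thresholds as clear and mandated whatever the suspected cause. Section 4.2.3.1 reports that in CMX001-301 subjects managed with interruptions had better outcomes than those dosed through persistent or worsening diarrhea. Interruptions for adverse events are a safety endpoint (Section 5.3.3) and part of the DSMB package (Section 4.5.1), so both would partly reflect which line a site followed.

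**Working it through.** The plan gives no figure to reproduce. The check applies each rule to the same course: a child who enters at Grade 2 or 3, reaches Grade 1 by Day 21, has never been interrupted, and then has diarrhea again at grade g.

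The rules as formulas:

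- A, from the Day 1 grade (parenthesis and Table 8): interrupt if g ≥ entry grade + 1.
- B, from the improved grade (general wording): interrupt if g ≥ improved grade + 1, here 1 + 1 = 2.
- C, Section 4.2.3.1: interrupt if g ≥ 2.

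| Entry grade | Returns at | A | B | C |
|---|---|---|---|---|
| 3 | 2 | continue | interrupt | interrupt |
| 3 | 3 | continue | interrupt | interrupt |
| 3 | 4 | interrupt | interrupt | interrupt |
| 2 | 2 | continue | interrupt | interrupt |
| 2 | 3 | interrupt | interrupt | interrupt |
| 2 | 4 | interrupt | interrupt | interrupt |

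For a Grade 3 entrant the threshold is 3 + 1 = 4 under A and 2 under B or C, a gap of two grades. For a Grade 2 entrant it is 2 + 1 = 3 against 2, a gap of one.

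If the child had improved to Grade 0, reading B would trigger at 0 + 1 = 1, while C would not. Section 8.3.2.1 lets dosing continue at Grade 1, so reading B has its own clash with the text.

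Next, does another rule cover this course?

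- 21-day check: passed, because the diarrhea was at Grade 1 or less in time.
- Recurrence after restart: not applicable, because BCV was never interrupted.
- Section 8.3.2.2: the onward reference from Section 8.3.2.1 leads here, but its scope excludes a child who entered at Grade 2 or 3.
- Table 8 footnote: it equates baseline with pre-transplant stool output, while the column headings use baseline for status at study entry. That adds a second meaning and does not settle the question.

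Timing: 4 to 6 weeks is Day 28 to Day 42 of treatment, which is 28 − 21 = 7 to 42 − 21 = 21 days after the 21-day check. That check cannot catch a return in this window.

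Who is still on BCV then? Section 4.3.3.2 gives a median time to undetectable viremia of 12 to 22 days in children, and Section 8.3.1 requires a confirmatory sample 7 to 14 days later. At the medians, stopping falls between about Day 12 + 7 = 19 and Day 22 + 14 = 36. In CMX001-304, among pediatric HCT recipients still on study, 59% were undetectable by Week 4 and 68% by Week 6 (Section 4.3.3.1), so 41% and 32% were not. Some children, not all, would still be dosed in the onset window.

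**The case against.** The best defense is that the parenthesis defines the worsening rule rather than illustrating it. If worsening means worse than Day 1, then Section 8.3.2.3, the Synopsis and Table 8 all agree. Section 11.9.1 fits that reading: signs present before the first dose count as adverse events only if they worsen by at least one grade afterwards. Section 7.3 requires management under Section 8.3.2, so it takes precedence over Section 4.2.3.1, which is background, phrased as a recommendation and limited to treatment-emergent diarrhea. Section 8.3.2 also names the Medical Monitor for questions.

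Much of this stands. A reader might infer that the operative texts cannot be reconciled with one another; they can, under the Day 1 reading. That reading is nowhere stated, however, and it departs from the principle in Section 4.2.3.1. It also treats two children with the same course from Day 15 differently because of entry grade alone. If that is intended, the protocol should say so. A call to the Medical Monitor does not replace a threshold described as mandated.

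The impact also has limits. Safety endpoints are generally not tested (Section 12.6), non-fatal AdV-related events need not be reported as adverse events (Section 11.9.1), and the method of the primary viremia analysis is unaffected. The CMX001-301 experience came from adults on CMV prevention and involved escalated steroids as well as continued dosing, so it does not carry over directly.

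**Conclusion.** The gap is real and should be closed before sites rely on these rules. Followed as written, Table 8 continues BCV through returned Grade 3 diarrhea in a Grade 3 entrant who had improved without interruption, whereas the general wording counted from the improved grade, and Section 4.2.3.1, lead to interruption at Grade 2. The passages must be reconciled; which action is clinically right is not for this review to say.

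Three stronger readings are not supported:

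- A reader might infer that Grade 2 entrants could also be dosed through Grade 3. They could not: Table 8 interrupts them at Grade 3, and only a return at Grade 2 is in dispute.
- A reader might want a headcount. The documents give no rate of AdV-attributed Grade 2 or 3 diarrhea at entry. The 57% diarrhea rate quoted from CMX001-202 is for any grade, in a BIW arm of 14 subjects, in a study of asymptomatic viremia that enrolled adults and children. It cannot be turned into a number for this trial.
- A reader might infer that every such child is exposed at Weeks 4 to 6. Some will already have stopped BCV on virologic clearance.

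The conclusion assumes that the Appendix 4 flow chart, which is not shown in the available text, and the reference card in the study reference manual do not already settle the point.

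**What to change.** State one reference grade for worsening in Section 8.3.2.3: the Day 1 grade or a defined on-treatment grade. If an on-treatment grade is chosen, say how a move from Grade 0 to Grade 1 is handled, given Section 8.3.2.1.

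Add one line to Table 8 for diarrhea that improved to Grade 1 or less without interruption and then returned, and clarify which meaning of baseline the table uses.

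Bring the Synopsis, Sections 4.2.3.1, 8.3.2.1, 8.3.2.2 and 8.3.2.3, and Table 8 into agreement, and check Appendix 4 and the reference card against them. The sponsor decides the clinical action; it must be the same in every place.

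The cost is protocol wording and site retraining. No new data or visits are needed.

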Pharmacokinetics: For subjects randomized to BCV, blood samples (5 samples collected pre-dose and up to 48 hours post-dose) will be collected on Day 1 and Week 2 (where blood volume loss limits allow) for analysis of plasma BCV concentrations by the designated bioanalytical laboratory. Samples collected from subjects who are receiving concurrent cyclosporine will also have cyclosporine concentrations analyzed. The Week 2 PK samples will only be collected if the subject remains on BCV therapy.

Safety Monitoring and Safety Reviews:

Prior clinical experience has shown that the main toxicities associated with BCV dosing are GI events, in particular diarrhea, and increase in serum aminotransferase concentrations. Investigators will be specifically trained on the management of BCV toxicity; subjects randomized to BCV therapy will be monitored for GI and hepatic abnormalities and managed as follows:

Treatment-emergent Grade 1 GI-related AEs:

Dosing with BCV may continue, while closely monitoring the subject for worsening of the AE(s). Symptomatic care may be provided as needed (e.g., anti-emetics, anti-diarrheals). Hydration status should be closely monitored, and liquid and electrolyte intake should be encouraged, if appropriate, to avoid dehydration and the downstream consequences of dehydration on renal function.

In the absence of extra-intestinal involvement, starting or increasing steroids and/or other immunosuppressants for the treatment of GVHD should be delayed if medically feasible for CTCAE Grade 1 diarrhea. If steroid treatment of GVHD cannot be delayed (and BCV is continued) in subjects with Grade 1 symptoms, the subject's response to GVHD therapy should be closely monitored.

If diarrhea persists for > 14 days at CTCAE Grade 1, the complete subject profile should be reviewed, other etiologies for diarrhea considered, and if deemed appropriate, interruption of BCV should be considered in order to determine whether diarrhea resolves.

Treatment-emergent Grade 2 or Higher Diarrhea in Subjects with \leq Grade 1 Diarrhea at Baseline:

For subjects enrolled with CTCAE Grade 1 diarrhea or no diarrhea at baseline, BCV must be interrupted for treatment-emergent CTCAE Grade 2 or higher diarrhea. This includes new-onset Grade 2 or higher diarrhea or progression from Grade 1 to Grade 2 or higher diarrhea, regardless of the cause of the diarrhea.

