8.3.2.1. Treatment-emergent Grade 1 GI-related AEs

Dosing with BCV may continue, while closely monitoring the subject for worsening of the AE(s).

Symptomatic care may be provided as needed (e.g., anti-emetics, anti-diarrheals). Hydration status should be closely monitored, and liquid and electrolyte intake should be encouraged, if appropriate, to avoid dehydration and the downstream consequences of dehydration on renal function.

Additionally:

- Nutritional advice should be given to avoid foods and drinks that affect intestinal water transport (e.g., caffeine, alcohol, carminative spices, and concentrated sugar syrups) as well as lactose- and sucrose-containing drinks because intestinal inflammation may result in down-regulation of intestinal disaccharidases
- Consideration should be given to adjusting medications associated with GI effects (e.g., macrolide antibiotics, magnesium sulfate salts and mycophenolate mofetil [MMF])
- Other causes of new GI symptoms should be investigated promptly and treated as appropriate (e.g., infections)

For treatment-emergent Grade 1 GI AEs, aggressive treatment of GVHD should be initiated only if the diagnosis is confirmed at another organ site (e.g., skin or liver). GI biopsy results, if endoscopy and biopsy are performed, may not differentiate GVHD from BCV-related toxicity because GI biopsies from subjects with BCV GI toxicity may show findings (such as crypt apoptotic bodies) that are also observed in biopsies from subjects with GVHD. If the subject is experiencing GVHD symptoms in other organ systems (e.g., skin or liver), biopsy specimens from those sites may be more informative.

In the absence of extra-intestinal involvement, starting or increasing steroids and/or other immunosuppressants for the treatment of GVHD should be delayed if medically feasible for Grade 1 diarrhea.

If steroid treatment of GVHD cannot be delayed (and BCV is continued) in subjects with Grade 1 symptoms, the subject's response to GVHD therapy should be closely monitored.

- If diarrhea persists for > 14 days at Grade 1, the complete subject profile should be reviewed, other etiologies for diarrhea considered, and if deemed appropriate, interruption of BCV should be considered in order to determine whether diarrhea resolves.

If diarrhea worsens to Grade 2 or higher, please see Section 8.3.2.2 below.

8.3.2.2. Treatment-emergent Grade 2 or Higher AEs of Diarrhea in Subjects with ≤ Grade 1 Diarrhea at Baseline

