Grade 2: Increase of 4 to 6 stools per day over baseline; or moderate increase in ostomy output compared to baseline

Grade 3: Increase of \geq 7 stools per day over baseline; incontinence; hospitalization indicated; or severe increase in ostomy output compared to baseline; limiting self-care activities of daily living (ADLs)

Grade 4: Life-threatening consequences; urgent intervention indicated

Note: Action taken with BCV is regardless of the etiology of diarrhea.

Note: Pre-transplant stool output (= baseline).

Table 9: Recommended Management/Evaluation of Treatment-emergent GI Adverse Events during BCV Therapy

	Grade 1 Events	Grade 2 or Higher Events
Action with BCV	See Table 8 and Section 8.3.2	
Other interventions	
 • Avoid food/drinks that affect water transport (e.g., caffeine, alcohol, carminative spices, concentrated sugar syrups) • Avoid lactose- and sucrose-containing products • Adjust other medications associated with GI effects (e.g., macrolides, magnesium, MMF) • Symptomatic treatment dosed as needed (e.g., anti-emetics, anti-diarrheals) • Avoid starting steroid/immunosuppressants for GVHD (while dosing BCV) unless Grade 1 diarrhea persists for > 14 days 	
 • Same as for Grade 1 events • Interrupt other medications that may cause GI events (e.g., magnesium supplements, MMF) • Measure levels of immunosuppressants • Consider symptomatic treatment (e.g., anti-emetics, anti-diarrheals) dosed at regular intervals, if clinically appropriate • Fluid supplementation to maintain hydration
Other diagnostic evaluations	
 • Monitor hydration status, and supplement as needed • Evaluate for other infection • Evaluate for acute GVHD in other organ systems; consider non-GI biopsy 	
 • Same as for Grade 1 events

NOTE: When considering new-onset or worsening GI GVHD as the cause of GI symptoms:

- **Co-administration of BCV and steroids for GI GVHD is not recommended**
- In order to assess response to BCV treatment interruption, start of (or increase in) **steroid therapy for GI GVHD should be delayed, when possible**

If diarrhea does not improve following ≥ 7 days interruption (i.e., at least 6 full days off BCV), a trial of steroid therapy for new or worsening GI GVHD (while BCV is still being held) may be considered, if deemed clinically appropriate.

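### Table 9's Grade 1 cell ends the advice against starting steroids on continued brincidofovir after 14 days of diarrhea, contrary to the note in the same table (minor wording error in advisory text)

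*Combined protocol and SAP*

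**What the plan says.** Table 9 (Section 8.3.2.3) gives recommended management for gastrointestinal events in the BCV arm. Its first row, on what to do with BCV, refers to Table 8 and Section 8.3.2. Its row on other interventions says, for Grade 1: "Avoid starting steroid/immunosuppressants for GVHD (while dosing BCV) unless Grade 1 diarrhea persists for > 14 days".

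The note that closes Table 9 says "Co-administration of BCV and steroids for GI GVHD is not recommended". It adds that if diarrhea has not improved after at least 7 days of interruption, "a trial of steroid therapy for new or worsening GI GVHD (while BCV is still being held) may be considered".

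Section 8.3.2.1, which governs Grade 1 events, makes three relevant statements:
- On GVHD treatment in general: "aggressive treatment of GVHD should be initiated only if the diagnosis is confirmed at another organ site". Without disease outside the gut, steroids are to be put off where feasible.
- On the exception: "If steroid treatment of GVHD cannot be delayed (and BCV is continued) in subjects with Grade 1 symptoms", the response to GVHD therapy is to be watched closely.
- On diarrhea beyond 14 days: the case is reviewed, other causes are considered and, if judged appropriate, "interruption of BCV should be considered in order to determine whether diarrhea resolves".

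The synopsis agrees: "If diarrhea persists for > 14 days at CTCAE Grade 1, the complete subject profile should be reviewed", with interruption then to be considered.

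Table 8, for children with Grade 1 diarrhea or none at baseline, says: "Consider interruption for Grade 1 diarrhea if persists for > 14 days, and starting treatment for acute GVHD".

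**The concern.** The cell and the note answer the same question differently. A site working from the cell may conclude that, after two weeks of mild diarrhea, steroids can be started with BCV continuing. A site working from the note would hold BCV first.

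The sequence matters because of Study CMX001-301. Section 4.2.3.1 describes corticosteroids given for diarrhea while BCV went on, continued diarrhea that was taken for refractory GVHD, and then heavier immunosuppression with worse outcomes. Section 4.4 repeats that attribution. Section 4.3.1 makes assessing the revised management guidance a primary objective, and Section 4.3.7 says immunosuppressant use will be recorded to show that the earlier steroid overuse has been curbed. Guidance that disagrees with itself on this step weakens both the protection and the assessment.

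**Working it through.** The check is a comparison of texts. Take a child in the BCV arm with Grade 1 diarrhea for more than 14 days, suspected GVHD of the gut only, and steroids that could wait.

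| Place | What more than 14 days triggers | Steroids while BCV continues? |
|---|---|---|
| Table 9, Grade 1 cell | The advice to avoid steroids ends | No longer advised against |
| Table 9, note | Nothing; no duration rule | Not recommended for gut GVHD; steroid trial only with BCV held |
| Section 8.3.2.1 | Review; consider interrupting BCV | Contemplated only when steroids cannot wait |
| Synopsis | Review; consider interrupting BCV | Same as Section 8.3.2.1 |
| Table 8, Grade 1 bullet | Consider interrupting BCV, with an unclear clause about GVHD treatment | Not stated |

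1. The cell and the note conflict for this child. The cell speaks of GVHD generally and the note of gut GVHD, but the cell's trigger is diarrhea, so suspected gut GVHD falls within it.
2. Section 8.3.2.1 does not supply the cell's exception. Its allowance for steroids with BCV continued rests on clinical urgency, not on duration, and it reserves aggressive treatment for GVHD confirmed at another site.
3. The pointer to Table 8 does not remove the conflict. Table 8 asks only that interruption be considered; a site can consider it, decline, and still rely on the cell. Table 8's closing clause can be read as a second condition for interruption, which the synopsis does not have, or as a condensed form of the Section 8.3.2.1 text.

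**When the conflict can arise.** The documents allow a time window but not a count.
- Typical pediatric onset of diarrhea is 4 to 6 weeks after starting BCV (Section 4.3.1), that is Day 28 to 42. Adding 14 days: 28 + 14 = 42 and 42 + 14 = 56, so the cell applies after about Day 42 to 56.
- Median time to undetectable viremia was 12 to 22 days in pediatric subjects of CMX001-304 (Section 4.3.3.2). The confirmatory sample follows 7 to 14 days later (Section 8.3.1). So 12 + 7 = 19 and 22 + 14 = 36: BCV stops at about Day 19 to 36, before allowing for laboratory reporting time.
- A child with median clearance and typical onset is therefore already off BCV. The conflict concerns slow clearers, early-onset diarrhea and re-treated children.
- On slow clearance, Table 4 gives pediatric responders at Week 6 as 17/25 + 28/41 = 45/66 = 68%, which matches Section 4.3.3.1. The remaining 66 − 45 = 21 (21/66 = 32%) were not undetectable. This covers one of several conditions that must coincide. It also comes from a study that included disseminated disease, so the share here may be lower.

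**The case against.** The strongest reply is that Table 9 already leads the reader to a hold. Its first row sends the reader to Table 8, which names interruption at this same 14-day point, and the note follows in the same table. The cell sits under other interventions and does not decide BCV dosing; lifting an instruction to avoid something does not recommend it. All the wording is advisory, investigators are trained in BCV toxicity management (Section 8.3), and the medical monitor can be asked (Section 8.3.2). Much of this stands. Holding BCV first was probably the intent, and that is why the point is minor. It does not make the cell correct, because the cell states an exception that the note lacks.

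A second reply is that the note's steroid-trial sentence closely follows Section 8.3.2.2, which covers Grade 2 or higher, whereas Section 8.3.2.1 contemplates steroids with BCV continued at Grade 1. This stands in part: the plan does not bar the combination at Grade 1. But the note is not limited by grade, and Section 8.3.2.1 ties its allowance to urgency.

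Third, the Appendix 4 flow chart is not shown in the text reviewed, and the reference cards are in the study reference manual. Either may state the sequence clearly, so actual confusion at sites has not been shown.

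**Conclusion.** The Table 9 Grade 1 cell is wrong as written. It contradicts its own table's note and does not match Section 8.3.2.1 or the synopsis. The error is minor: one cell of an advisory table, with interruption at Grade 2 or higher unaffected.

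A reader might infer three stronger things that the documents do not support.
- **That the protocol tells sites to combine steroids with BCV after 14 days.** It does not; the cell withdraws a caution, and the first row and the note point toward holding BCV.
- **That a hold of at least 7 days must always precede steroids at Grade 1.** The synopsis and Section 8.3.2.1 ask only that interruption be considered, and the latter contemplates urgent steroids with BCV continued.
- **That about a third of BCV children are exposed.** The 21/66 figure counts slow clearance alone. It says nothing about prolonged Grade 1 diarrhea, suspected gut-only GVHD or steroids that could wait. The number affected cannot be estimated.

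The harm is by analogy. CMX001-301 was an adult CMV prevention trial, its steroid figures are not specific to Grade 1 diarrhea, and Section 4.2.3.1 says pediatricians tend to treat presumptive GVHD less aggressively during adenovirus viremia. The correction is still worth making, because it is cheap and concerns the pattern the protocol itself blames for poor outcomes.

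**What to change.** 1. **Table 9, Grade 1 cell.** Remove the duration exception. Suggested text: *Avoid starting steroids/immunosuppressants for GI GVHD while dosing BCV, unless GVHD is confirmed at another organ site or treatment cannot be delayed (Section 8.3.2.1). If Grade 1 diarrhea persists for > 14 days, review other causes and consider interrupting BCV (Table 8) before starting steroids; see note.*
2. **Table 8, Grade 1 bullet.** Suggested text: *Consider interruption if Grade 1 diarrhea persists for > 14 days, and before starting treatment for GI GVHD.* Keep the word *consider*; making the hold mandatory would put the tables at odds with the synopsis and Section 8.3.2.1.
3. **Table 8, Resumption row.** The present test is improvement to Grade 1 or below, which a child held at Grade 1 already meets in grade. State that such a child may resume on improvement or no worsening after at least 7 days off BCV.
4. Check that Appendix 4, the reference cards and the training material match.

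The cost is three short edits in two tables and the matching site material. The clinical downside is that some possibly viremic children may be held who would otherwise have continued. With doses 3 and 4 days apart, a restart 7 days after the last dose misses at least one twice-weekly dose, and Table 8 then requires the once-weekly schedule. If a steroid trial follows with BCV still held, the gap is longer. The decision stays with the investigator, as the plan already allows.
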